2.3 ENDPOINTS

Primary endpoint:

- The presence or absence of systemic exposure to cantharidin by the collection and analysis of plasma samples from patients with 21 or more molluscum lesions following treatment of VP-102.

Secondary endpoint:

- Proportion of subjects exhibiting complete clearance of all treated molluscum lesions (baseline and new) on or before Week 12 (EOS).

Exploratory endpoints:

- Proportion of subjects exhibiting a 90% or greater reduction of all treated molluscum lesions (baseline and new) at the EOS visit.
- Percent reduction of treated molluscum lesions from baseline at the EOS visit.
- Change from baseline in the number of treated molluscum lesions at the EOS visit.
- Change from baseline in quality of life and impact of skin disease as measured by the CDLQI assessment.

- Spread to siblings as measured by any new occurrence of molluscum in siblings of the subject.

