7.2.2 Sample Size

The primary objective of the study is to determine the presence or absence of systemic cantharidin exposure from application of VP-102. Thus, power calculations were not performed. Data will be summarized using descriptive statistics (sample size, mean, median, standard deviation, minimum, maximum) for continuous variables and frequencies and percentages for discrete variables. Corresponding by-subject data listings will be tabulated. There will be up to 40 subjects enrolled with the goal of 16 completing all blood draws in the exposure group. A maximum of 16 will be enrolled in the standard treatment group. The additional 8 subjects may be used for replacement patients. Any subject in the exposure group who does not complete all blood draws may continue to receive treatment, but will be replaced. No more than 16 subjects will be considered as completed Exposure group participants. At least 3 patients in the exposure group will be from 2-5 years of age. The definition of an enrolled will be those subjects that have signed informed consent and have been treated with at least 1 treatment.

Analysis Populations

Exposure Population: The Exposure population will include all subjects who have valid blood samples measured to assess exposure. This population will be used for the exposure analysis.

Intent-to-Treat Population: The intent-to-treat population (ITT) will include all subjects who meet the screening eligibility criteria and are enrolled in the study. This population will be used for the efficacy analysis.

Safety Populations: The safety population will include subjects who meet the screening eligibility criteria for the study and receive at least one application of Study drug. This population will be used for the safety analysis.

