The analyses described in this plan are considered *a priori*, in that they have been defined prior to database lock. Any analysis added after the database lock will be considered *post hoc* and exploratory. *Post hoc* analyses will be labeled as such on the output and identified in the CSR. All analyses and tabulations will be performed using SAS® version 9.3 or higher. Tables and listings will be presented in .rtf or .pdf format. Upon completion, all SAS programs will be validated by an independent programmer. The validation process will be used to confirm that statistically valid methods have been implemented and that all data manipulations and calculations are accurate. Checks will be made to ensure accuracy, consistency with this plan, consistency with tables and consistency between tables and corresponding data listings.

6. Analysis Populations

The Intent to Treat population (ITT) will include all subjects who meet the screening eligibility criteria and are enrolled in the study. A subject will be considered enrolled in the study when they have signed informed consent and received at least 1 treatment of study medication.

The Safety population will include subjects who meet the screening eligibility criteria for the study and receive at least one application of Study drug.

The Exposure population will include those subjects who are assigned to the Exposure cohort and have successfully completed all blood draws (Pre-Application and 2hr, 6hr and 24hr post-application on Day 1). Subjects assigned to the Exposure cohort without successfully completing all blood draws will be replaced and not included in the Exposure population, but will be included in the Intent to Treat and Safety populations.

7. Study Population

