7.3. Demographic and Baseline Characteristics

Demographics variables will include: age, sex, ethnicity and race. Age will be calculated by comparing date of birth to date of informed consent.

Baseline characteristics will include: medical history, molluscum history, height, weight and body mass index (BMI). BMI will be calculated by weight (kg) / height (m^2). Molluscum history variables that will be summarized include time since clinical diagnosis (as compared to informed consent), age at diagnosis and any previous treatments for molluscum lesions. Medical history will not be summarized in a table, but will be displayed in a listing.

Continuous variables will be summarized using descriptive statistics. Categorical variables will be summarized using counts and percentages. Demographics, baseline characteristics and molluscum history will be summarized for all 3 analysis populations (ITT, Safety, Exposure).

8. Exposure Analysis

Plasma samples from the Exposure group will be analyzed at each time point using a GC/MS assay method that was previously validated by Pacific Bio Labs (Study number 14I0376R-A03). Samples will be listed as either below or above the LLOQ (1 ng/ml).

An overall and by time point summaries of concentration results above and below the LLOQ will be provided using the Exposure population. Concentration levels above LLOQ will be considered evidence of the presence of systemic cantharidin (primary objective). A listing will be generated which will show results of LLOQ as well as any results reported above LLOQ.

9. Efficacy Analysis

The ITT and Exposure population will be used for efficacy analysis. Results will be summarized using descriptive statistics and counts/percentages. Where appropriate, 95% confidence intervals may be generated as well.

For the purposes of the analyses, all lesions reported in the study will be considered treatable. Although the protocol specifies study objectives and efficacy variables in terms of treated lesions, actual analysis will be carried out on treatable lesions. The reason to carry out analysis on treatable lesions is to avoid any bias or confusion with determining whether a lesion was treated. This is also in alignment with other studies in this clinical program per regulatory feedback. As a result, considering treatable lesions instead of treated lesions will be a more conservative approach when analyzing study results.

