9.4. Handling of Dropouts or Missing Data

All subjects who receive treatment will be evaluated in the ITT population. Subjects who do not complete all of the scheduled blood draws will be replaced. In the event a subject requests to be removed from the study due to study related adverse events or additional spreading of disease, data will be collected and analyzed as a treatment failure and not replaced.

Unless described otherwise in subsequent sections, analyses will be carried out with the data available using no imputation for missing data. A description of how missing data will be handled for the primary endpoint and secondary endpoints is included below.

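### SAP section 6 limits the Exposure population to four-draw completers without giving a reason, so a measured positive in a subject who missed one draw is left out of the primary LLOQ summary

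*SAP*

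**What the plan says.** The two documents define the Exposure population differently.

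- **Protocol 7.2.2 (Analysis Populations):** "The Exposure population will include all subjects who have valid blood samples measured to assess exposure". This population is assigned to the exposure analysis.
- **Protocol 2.3:** the primary endpoint rests on "collection and analysis of plasma samples from patients with 21 or more molluscum lesions following treatment of VP-102". It sets no condition on the number of draws.
- **Protocol 2.2, 2.4 and 7.2.2:** completing all draws is the enrolment goal (16 subjects), and failing to do so triggers replacement.
- **SAP section 6:** the population is limited to Exposure-cohort subjects with the pre-application, 2-, 6- and 24-hour draws all completed. For the rest: "Subjects assigned to the Exposure cohort without successfully completing all blood draws will be replaced and not included in the Exposure population". They stay in the ITT and Safety populations.
- **SAP section 8:** "An overall and by time point summaries of concentration results above and below the LLOQ will be provided using the Exposure population". A level above LLOQ (1 ng/ml) is taken as evidence that the drug is systemically present, in a sentence that names no population. There is also a listing: "A listing will be generated which will show results of LLOQ as well as any results reported above LLOQ".
- **SAP section 5:** every summary table shows the Exposure and Standard groups, plus a total that includes replaced subjects.
- **SAP 9.4:** by default, "analyses will be carried out with the data available using no imputation for missing data". It adds: "A description of how missing data will be handled for the primary endpoint and secondary endpoints is included below".

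**The concern.** The SAP turns a rule about whom to replace into a rule about whose plasma results enter the primary summary, and it gives no reason. Elsewhere it does explain a departure from the protocol: section 9 sets out why lesions are analysed as treatable and not as treated.

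For a presence/absence endpoint, one valid post-application result above LLOQ bears directly on the answer. A missed draw weakens the case that a subject was negative, but it does not undo a positive that was measured. Negative non-completers are dropped too, so a percentage can move either way. Dropping subjects can never create a positive, however, so the reading of the summary can change only from present to absent.

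The listing would still show the positive, so the conclusion is not necessarily reversed. What is at stake is a primary table that reads as no detection beside a listing that shows one, with nothing to say which decides the primary objective.

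**Working it through.** **The plan's own figure.** Protocol 7.2.2 gives 16 exposure completers, at most 16 standard-treatment subjects and 8 further subjects for replacement: 16 + 16 + 8 = 40, the stated enrolment cap. No power, alpha, dropout or detection rate is stated, so the rates below are assumptions.

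**Tracing one subject through the SAP.** Take a dosed Exposure-group subject with valid 2-, 6- and 24-hour results, one of them above LLOQ, and no pre-application sample. Under protocol 7.2.2 the subject has valid measured samples and is in. Under SAP section 6 the subject is replaced and out. The section 8 overall and by-time-point summaries omit the positive; the section 8 listing shows it. Section 9.4 adds no rule for this case: 9.4.1 and 9.4.2 deal only with clearance, lesion counts and CDLQI.

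**Effect on the summary.** Suppose one replaced subject is positive and no completer is. The intervals are exact (Clopper-Pearson) 95% and illustrative, since section 8 plans none.

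- SAP set: 0/16 = 0%. Upper limit 1 − 0.025^(1/16) = 20.6%.
- All sampled subjects: 1/17 = 5.9%. Interval 0.15% to 28.7%.

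**Valid post-application results left out.** The completers supply 16 × 3 = 48. A replaced subject who misses one draw supplies 2 (a post-application draw missed) or 3 (only the pre-application draw missed). With k such subjects the excluded share runs from 2k/(48 + 2k) to 3k/(48 + 3k):

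- k = 1: 2/50 to 3/51, 4.0% to 5.9%
- k = 2: 4/52 to 6/54, 7.7% to 11.1%
- k = 8: 16/64 to 24/72, 25.0% to 33.3%

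**Chance of the damaging pattern.** Let p be the true subject-level detection rate and h the share of positives that fall in the samples actually taken, with subjects independent:

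P(0 of 16 completers positive, at least 1 of k replaced positive) = (1 − p)^16 × [1 − (1 − hp)^k]

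Example with p = 0.05, k = 2, h = 1: 0.95^16 × (1 − 0.95^2) = 0.4401 × 0.0975 = 4.29%.

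| k | h | p = 2% | p = 5% | p = 10% |
|---|---|---|---|---|
| 1 | 1 | 1.45% | 2.20% | 1.85% |
| 2 | 1 | 2.87% | 4.29% | 3.52% |
| 8 | 1 | 10.80% | 14.81% | 10.55% |
| 1 | 0.5 | 0.72% | 1.10% | 0.93% |
| 2 | 0.5 | 1.44% | 2.17% | 1.81% |
| 8 | 0.5 | 5.59% | 8.07% | 6.24% |

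The value h = 1 fits a subject who missed only the pre-application draw. If a post-application draw was missed, h is lower.

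**The case against.** The best defence is that the SAP settles an ambiguity in the protocol, openly and in advance. Protocol 7.2 lets the SAP modify the analysis, and the protocol never defines a valid sample. Protocol 2.4 says subjects with missed draws who continue are evaluated for efficacy and safety, and does not mention exposure; 2.2 and 7.2.2 cap completed exposure participants at 16. Requiring full profiles also has scientific merit: a positive without a pre-application sample is harder to attribute to the application, and a partial profile is weak support for absence. Section 8's evidence sentence is not limited to any population, so a listed positive could still count. Section 5's total, which includes replaced subjects, could be read as bringing these subjects back. The scenario is also improbable with few replacements.

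Much of this stands as qualification. The SAP is entitled to make the change, section 6 does work as an exclusion rule, the positive is not lost, and the probabilities are small and rest on assumptions.

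It does not remove the problem. Protocol 2.4 nowhere says that plasma already measured leaves the exposure analysis. Permission to change is not a reason for the change. Section 5 is a general table rule whose companion requirement, a Standard-group summary, cannot fit a table of plasma drawn in one group only. Section 8 specifically names the Exposure population. Section 5 needs clarifying for this table; it neither overrides section 8 nor firmly contradicts it. The attribution difficulty calls for a flag, not for exclusion.

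**Conclusion.** The concern holds. Followed as written, SAP sections 6 and 8 leave a measured post-application positive in a non-completer out of the primary LLOQ summary. The population is narrower than the protocol's, no reason is given, and any change in the presence/absence reading is toward absence.

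The likely size is modest. With one or two replacements the chance that the table shows 0/16 while a replaced subject is positive is about 1% to 4% (0.7% to 4.3% over the cases shown). It reaches about 15% only if all 8 replacement slots are used, which is an extreme case. These figures assume detection rates of 2% to 10%, independence between subjects, and half or all of the positives falling in samples actually taken. Because the listing would still show the result, the practical harm is a primary table and a listing that may disagree with no rule between them. It should be corrected because it touches the primary endpoint and can be settled by wording alone.

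**What to change.** In SAP section 8, with section 6 aligned:

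1. Base the primary presence/absence summary on all dosed Exposure-group subjects with at least one valid post-application plasma result, with the available n as denominator at each time point. This cutoff is a proposed way to make the protocol's definition operational, and it matches the available-data default in SAP 9.4.
2. State that any post-application result above LLOQ in any dosed subject counts as presence, and flag any such subject without a pre-application result.
3. Keep four-draw completion as the replacement criterion, and show the completers in a supporting table for any statement of absence.
4. Add one sentence in section 5 on how the total that includes replaced subjects applies to this table.

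This should be done before database lock, since section 5 treats analyses added later as post hoc.

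The cost is wording in sections 5, 6 and 8 and one extra table; no new data or subjects are needed. Some counted subjects will have incomplete profiles, which support absence less well. A positive without a pre-application sample will be harder to attribute, and denominators will vary by time point.

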7.1. Subject Disposition

Information regarding subject disposition will be summarized for all subjects by treatment group. Summaries will include: number of subjects enrolled, number of subjects in each analysis population, number of subjects completing the study, and number of subjects who discontinue the study early. For those who discontinue early, the primary reason for discontinuation will be summarized.

7.2. Protocol Deviations

Protocol deviations will be collected throughout the duration of the study. Protocol deviations will be assigned a sponsor-defined category type. Each deviation will be defined as major or minor. A tabular summary of all major deviations will be generated. In addition, a by-subject listing of all protocol deviations (major and minor) will be produced.

7.3. Demographic and Baseline Characteristics

Demographics variables will include: age, sex, ethnicity and race. Age will be calculated by comparing date of birth to date of informed consent.

Baseline characteristics will include: medical history, molluscum history, height, weight and body mass index (BMI). BMI will be calculated by weight (kg) / height (m^2). Molluscum history variables that will be summarized include time since clinical diagnosis (as compared to informed consent), age at diagnosis and any previous treatments for molluscum lesions. Medical history will not be summarized in a table, but will be displayed in a listing.

Continuous variables will be summarized using descriptive statistics. Categorical variables will be summarized using counts and percentages. Demographics, baseline characteristics and molluscum history will be summarized for all 3 analysis populations (ITT, Safety, Exposure).

8. Exposure Analysis

Plasma samples from the Exposure group will be analyzed at each time point using a GC/MS assay method that was previously validated by Pacific Bio Labs (Study number 14I0376R-A03). Samples will be listed as either below or above the LLOQ (1 ng/ml).

An overall and by time point summaries of concentration results above and below the LLOQ will be provided using the Exposure population. Concentration levels above LLOQ will be considered evidence of the presence of systemic cantharidin (primary objective). A listing will be generated which will show results of LLOQ as well as any results reported above LLOQ.

9. Efficacy Analysis

The ITT and Exposure population will be used for efficacy analysis. Results will be summarized using descriptive statistics and counts/percentages. Where appropriate, 95% confidence intervals may be generated as well.

For the purposes of the analyses, all lesions reported in the study will be considered treatable. Although the protocol specifies study objectives and efficacy variables in terms of treated lesions, actual analysis will be carried out on treatable lesions. The reason to carry out analysis on treatable lesions is to avoid any bias or confusion with determining whether a lesion was treated. This is also in alignment with other studies in this clinical program per regulatory feedback. As a result, considering treatable lesions instead of treated lesions will be a more conservative approach when analyzing study results.

9.1. Efficacy Variables

Efficacy endpoints to be analyzed are:

- Proportion of subjects exhibiting complete clearance of all treated molluscum lesions (baseline and new) on or before Week 12 (EOS).
- Proportion of subjects exhibiting a 90% or greater reduction of all molluscum lesions (baseline and new) at the EOS visit.
- Percent reduction of molluscum lesions from baseline at the EOS visit.
- Change from baseline in the number of molluscum lesions at the EOS visit.
- Change from baseline in the quality of life and impact of skin disease as measured by the Children's Dermatology Life Quality Index (CDLQI) assessment at the EOS visit.
- Subject reported spread to siblings as measured by any new occurrence of molluscum in siblings of subject.

9.2. Baseline Values

Unless otherwise noted, baseline is defined as the last non-missing value recorded prior to the first application of study drug. When applicable, unscheduled visits will be used in the determination of baseline values.

9.3. Adjustments for Covariates

No statistical analysis is planned for this study; as a result, no adjustment for covariates will be made.

9.4. Handling of Dropouts or Missing Data

All subjects who receive treatment will be evaluated in the ITT population. Subjects who do not complete all of the scheduled blood draws will be replaced. In the event a subject requests to be removed from the study due to study related adverse events or additional spreading of disease, data will be collected and analyzed as a treatment failure and not replaced.

Unless described otherwise in subsequent sections, analyses will be carried out with the data available using no imputation for missing data. A description of how missing data will be handled for the primary endpoint and secondary endpoints is included below.

9.4.1. Handling of Missing Data for Complete Clearance Endpoint

The efficacy endpoint, proportion of subjects exhibiting complete clearance of all treatable lesions, is to be assessed a maximum of four times during the study. Assessments are to be done at Day 21, Day 42, Day 63 and Day 84 (EOS).

Subjects who do not have an assessment of complete clearance of all treatable lesions at any of the scheduled assessments will be considered to have missing data for this endpoint. Since the endpoint is complete clearance on or before Week 12, a subject will be considered to have met the condition of complete clearance if that subject has at least one assessment of complete clearance, regardless of what other assessments of clearance may be missing. If a subject has only non-missing assessments of not achieving clearance, then that subject will not be considered to have cleared. If a subject is missing all assessments of clearance, then that subject will be considered to have not cleared.

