
1. Are unable to cooperate with the requirements or visits of the study, as determined by the investigator.2. Have molluscum venereum (sexually transmitted molluscum).3. Have active molluscum eczema.4. Are systemically immunosuppressed or are receiving treatments such as chemotherapy or other non-topical immunosuppressive agents.5. Have had any previous treatment of molluscum in the past 14 days including the use of cantharidin, antivirals, retinoids, curettage or freezing of lesions. Additional treatments for molluscum should not be implemented during the course of the study.6. Have history of illness or any dermatologic disorder, which, in the opinion of the investigator will interfere with accurate counting of lesions or increase the risk of adverse events.7. History or presence of clinically significant medical, psychiatric, or emotional condition or abnormality that in the opinion of the investigator would compromise the safety of the subject or the quality of the data.8. Have a history or presence of hypersensitivity or an idiosyncratic reaction to the Study drug or related compounds, or drug product excipients (acetone, ethyl alcohol, nitrocellulose, castor oil, camphor, gentian violet, and denatonium benzoate).9. Have a condition or situation that may interfere significantly with the subject's participation in the study (e.g., patients who required hospitalization in the 2 months prior to screening for an acute or chronic condition including alcohol or drug abuse), at the discretion of the investigator.10. Have received another investigational product within 14 days prior to the first application of the Study drug.11. Have been treated within 14 days with a product that contains cantharidin (topical or homeopathic preparations) for any reason prior to screening.12. Are sexually active or may become sexually active and are unwilling to practice responsible birth control methods. Females that have reached menarche, must have a negative urine pregnancy test at screening and each visit prior to treatment with study medication.13. Are pregnant or breastfeeding.

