4.2.2 Evaluations (Treatment Day 1)

Subjects will return to the clinical site for screening if it was not completed previously, and the following evaluations will be performed:

1. Confirmation of eligibility.
2. Medical history to assess any changes since screening (as described in [Section 4.2.1](#)).
3. Review and recording of any concomitant medications and non-pharmacologic treatments or procedures in the last 14 Days prior to enrollment and since the last study visit.
4. Vital signs (heart rate and temperature).
5. Limited physical examination.
6. Dermatologic exam (as described in [Section 4.2.1](#)).
7. CDLQI assessment.
8. LSR assessment.

9. Urine pregnancy test for females of child bearing potential, defined as capable of menstruating, to determine protocol eligibility.
10. Photographs taken before application of the Study drug (at selected sites only).
11. Application of Study drug.
12. Review and record any AEs and concomitant medications.
13. Completion of PERIT assessment by parent or guardian approximately 24 hours following application of the Study drug.
14. Depending on age of subject, subject or parent/guardian will wash off the Study drug 24 hours post application of Study drug or when convenient after the 24 hour time point is reached provided there are no adverse reactions. Patients/guardians may gently remove the Study drug from lesions without the use of a washcloth in problematic areas prior to the expected 24 hours if the lesions have already blistered or if the patient is experiencing unmanageable pain. Study drug should not be removed from the additional lesions, where possible, until the expected blistering occurs or the 24 hour time point is reached, whichever comes first.
15. A follow-up phone call from the investigator or a designated member of the clinical research team will be conducted the following day after each treatment to allow parents/guardians to ask questions and report any concerns, confirm removal of Study drug, and review the completion of the PERIT assessment.

4.2.3 Evaluations: (Treatments Day 21, 42 and 63):

1. Review and recording of any concomitant medications and non-pharmacologic treatments/procedures since previous visit.
2. Review and recording of any AEs (before and after Study drug application).
3. Vital signs (heart rate and temperature) before Study drug application.
4. Dermatologic exam (as described in [Section 4.2.1](#)) with counting of molluscum lesions.
5. CDLQI assessment.

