6.0 STUDY OR SITE TERMINATION AND SUBJECT DISCONTINUATION

6.1 SUBJECT DISCONTINUATION

Subjects will be encouraged to complete the study; however, they may voluntarily withdraw at any time. The investigator will provide a written explanation of the reason for discontinuation in a source document and this information will be recorded on the appropriate CRF page. If a subject withdraws before completion, every effort should be made to complete the Day 84 assessments scheduled during the End of Study visit.

A subject may be removed from the study for the reasons described in [Section 6.1.1](#) through [Section 6.1.5](#).

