6.1.4 Refusal of Investigational Product Administration

Any subject refusing clinical trial material for any reason will be discontinued from the study, and the reason(s) will be documented on the appropriate CRF page. Reasonable efforts should be made to monitor the subject for AEs and to complete follow-up assessments after treatment discontinuation. These efforts should be documented on the appropriate CRF page.

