10.1. Complete Clearance of Treatable Lesions

Counts and percent of subjects who have complete clearance of all treatable molluscum lesions on or before EOS will be displayed by treatment group. Complete clearance will be defined as no lesions (lesion count=0) reported for a subject per the Skin Examination form. Summaries of complete clearance will also be provided by visit. Note: all lesions reported on the Skin Examination form will be considered treatable. Number of inflamed lesions, number of lesions not treated and reasons why lesions were not treated will be displayed in listings.

The EOS visit is scheduled to occur on Day 84 and 21 days (+/- 4 days) after their last treatment visit. For the analyses of this endpoint, only visits that occur prior to Day 100 will be considered for determining complete clearance. Subjects without an assessment of lesion count within this visit window will be counted as not cleared.

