11.7. Prior and Concomitant Medications

Prior and concomitant medication verbatim terms captured via the EDC system will be mapped to Anatomical/Therapeutic/Chemical (ATC) class and Preferred Names using the most current versions of the World Health Organization (WHO) Drug Dictionary Enhanced available.

Prior and concomitant medications will be summarized for each treatment group by WHO ATC class and preferred name. These summaries will present the number and percent of subjects using each medication. Subjects may have more than one medication per ATC class and preferred name. At each level of subject summarization, a subject is counted once if one or more medications at that level is reported for the subject. Each summary will be ordered by descending order of incidence of ATC class and preferred term.

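### The complete-clearance rule does not ask what removed the lesions, so a zero count after another molluscum treatment is scored as a VP-102 success

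*SAP*

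**What the plan says.** **Definition.** SAP 10.1: "Complete clearance will be defined as no lesions (lesion count=0) reported for a subject per the Skin Examination form". Visits before Day 100 count. SAP 9.4.1 adds that "a subject will be considered to have met the condition of complete clearance if that subject has at least one assessment of complete clearance", whatever other assessments are missing. SAP 9 counts all reported lesions as treatable, in place of the protocol's treated lesions.

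**Prohibition.** Exclusion criterion 5 in the protocol synopsis says: "Additional treatments for molluscum should not be implemented during the course of the study". Protocol 2.2.2 says nearly the same. The criterion names cantharidin, antivirals, retinoids, curettage and freezing among the earlier treatments that exclude a child.

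**Failure rule.** SAP 9.4, following Protocol 2.4, has one trigger: "In the event a subject requests to be removed from the study due to study related adverse events or additional spreading of disease". Such a subject is analysed as a treatment failure.

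**Assessment after stopping.** For a subject who withdraws early, Protocol 6.1 says that "every effort should be made to complete the Day 84 assessments scheduled during the End of Study visit". After refusal of VP-102, Protocol 6.1.4 asks for reasonable efforts "to complete follow-up assessments after treatment discontinuation".

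**Records and reporting.** Item 1 of Protocol 4.2.3 and of 4.2.4 requires: "Review and recording of any concomitant medications and non-pharmacologic treatments/procedures since previous visit". SAP 11.7 says: "Prior and concomitant medications will be summarized for each treatment group by WHO ATC class and preferred name". SAP 7.2 tabulates major protocol deviations and lists all deviations by subject.

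**The concern.** The secondary efficacy objective is to assess VP-102. The study has no control arm and plans no formal comparison (SAP 9.6), so the clearance proportion will be read directly as what the drug achieved. The protocol treats other molluscum therapy as incompatible with that reading and forbids it. The SAP does not carry the prohibition into the endpoint: if the forbidden treatment happens and works, the child becomes a responder. The same lesion counts feed the endpoints of at least 90% reduction, change and percent change (SAP 9.4.2, 10.2, 10.3), so they share the gap.

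**Working it through.** The plan gives no power, alpha, effect size or expected clearance rate, so there is no figure of its own to reproduce. The check is a reading of the rules, followed by simple arithmetic for scale.

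**1. How each case is scored.** Suppose a child has another molluscum treatment and then a zero count before Day 100.

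| Child | Rule that applies | Score as written |
|---|---|---|
| Asks to leave because of study-related adverse events or spread | SAP 9.4 | Failure, although the SAP does not say whether this overrides a zero count under 9.4.1 |
| Stays in the study | SAP 9.4.1, 10.1 | Cleared |
| Refuses a later application, without a request to leave for the reasons above | SAP 9.4.1, 10.1 | Cleared |
| Discontinued by the investigator (Protocol 6.1.1 to 6.1.3) | SAP 9.4.1, 10.1 | Cleared |

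**2. Is there another safeguard?** Efficacy uses the ITT and Exposure populations (SAP 9), and SAP 6 defines no per-protocol population. SAP 7.2 reports deviations but gives them no effect on responder status. Protocol 7.2.7 refers missing-data handling to the SAP, and the SAP is silent on this event.

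**3. Could a later count correct the score?** No. One zero is enough. A child still in the study who reaches zero also has the EOS visit that day (Protocol 2.1, SAP 3), so follow-up ends there.

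**4. Direction.** Compare the rule as written with one that scores these children as non-responders. The only possible move is from not cleared to cleared, so the proportion can rise but never fall.

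**5. Size.** Inputs are from Protocol 7.2.2: 16 exposure completers, up to 16 standard-treatment subjects and 8 possible replacements, and 16 + 16 + 8 = 40. With k affected subjects among n, the shift is k/n. For k = 1:
- n = 16: 1/16 = 6.25 points
- n = 32 (16 + 16): 1/32 = 3.1 points
- n = 40: 1/40 = 2.5 points

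**6. Size against precision.** Assume a 50% clearance rate for illustration (the documents give none) and use exact Clopper-Pearson 95% intervals. Rescoring one subject gives:
- n = 16: 8/16 = 50.0% (24.7% to 75.3%) becomes 7/16 = 43.8% (19.8% to 70.1%)
- n = 40: 20/40 = 50.0% (33.8% to 66.2%) becomes 19/40 = 47.5% (31.5% to 63.9%)

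One subject moves the estimate by far less than the width of its interval, but always in the same direction.

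**The case against.** The strongest reply is that using observed counts in all treated subjects, whatever else they received, is a recognised treatment-policy approach, and that the prohibition should make such cases rare. Part of this stands. The approach would be defensible if the SAP chose it openly, but it does not. Its one failure rule points the other way, since leaving for adverse events or spread already counts against the drug. SAP 9 calls the switch to treatable lesions more conservative, but that switch does not deal with lesions removed by other means.

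Three stronger readings are tempting, and the documents do not support them.
- *Such treatments would go unreported.* SAP 11.7 tabulates medications and not procedures. But a forbidden procedure is a protocol deviation, so SAP 7.2 would list it and, if it is classed as major, tabulate it. Antivirals, retinoids and other drugs would appear in the 11.7 table. What stands is that neither output changes the score.
- *Withdrawn children are meant to return at Day 84 after treatment elsewhere.* Protocol 6.1 and 2.3.1 can equally be read as asking for the EOS assessments at the time of withdrawal. Protocol 6.1.4 leaves the timing open. The route is possible, but it is not planned.
- *The bias comes from children in whom VP-102 was abandoned.* A child who remains on VP-102 can be affected, and some who abandon it are already failures under SAP 9.4.

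**Conclusion.** The gap is real and of modest weight. As written, SAP 10.1 and 9.4.1 credit VP-102 with any zero count before Day 100, including one that follows a forbidden treatment, except perhaps in the one group covered by SAP 9.4. The error can only favour the drug.

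Each affected subject adds 6.25 points at n = 16, 3.1 at n = 32 or 2.5 at n = 40. These are per-subject figures and not a forecast. A reader might multiply them by one or two cases per group and quote an expected inflation, but nothing in the documents supports any count, and it may be zero.

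Clearance is a secondary endpoint, and the lesion-reduction endpoints are exploratory (Protocol 2.3). All are descriptive, and no test or sample size depends on them. The primary plasma endpoint is unaffected. The change should be made because it is cheap and has to be settled before the data are seen.

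**What to change.** Amend SAP 10.1, 9.4.1 and 9.4.2 before database lock.

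- **Clearance and at least 90% reduction:** lesion counts taken after the start of another molluscum-directed drug or procedure do not count. The subject is a non-responder unless the criterion was met before that date.
- **Change and percent change:** state the handling in advance, for example the last count before the other treatment, and show the as-observed result beside it.
- **Reporting:** list the affected subjects with the treatment and its timing. Keep the as-observed summaries as a sensitivity analysis.
- **SAP 9.4:** say whether the treatment-failure rule overrides an earlier or later zero count.

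No new data are needed. Medications and procedures are already recorded at Days 21, 42 and 63 and at EOS. Because lesions are counted only at visits, knowing between which visits the other treatment fell is enough. The work is SAP wording and one derivation, and it does not alter how any child is managed.

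There is a price. The clearance proportion may be slightly less favourable, and a child with a single lesion treated elsewhere would be scored against the drug. The as-observed summary shows how much depends on that choice.
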